8.4 Swelling Assessment

Swelling measurements will be taken at each in-clinic visit (Appendix C). The measurements will be completed by research personnel with documented training showing the individual was able to independently and accurately conduct the measurements on 2 occasions.

8.5 Symptom Assessment

Symptoms will be assessed at each in-clinic visit using the EORTC H+N35 (Appendix E). The survey will be completed by the subject.

8.6 Quality of Life & Pain Assessment

Quality of Life will be assessed at each in-clinic visit using the EORTC C30 (Appendix D). The survey will be completed by the subject.

Pain will be assessed at each in-clinic visit using the VAS (Appendix F). The assessment will be completed by the subject.

8.7 Device Use Evaluation

During the phone follow-up at Visit 3 and 5, site research personnel will ask the subject questions about device use to evaluate if additional device training by Tactile personnel is warranted.

8.8 **Ease of Use and Treatment Satisfaction**

Ease of use and treatment satisfaction will be assessed by survey (Appendix G). The survey will be completed by the subject.

8.9 **Compliance Assessment**

Compliance with device treatment may be assessed at each in-clinic and phone follow-up visit. The subject may be asked to record compliance in a diary (Appendix H), or device use data may be downloaded periodically for subjects using the Flexitouch Plus.

8.10 **Adverse Event Reporting & Device Observations**

Reportable events, as defined below, will be recorded in the subject's medical record and on the Adverse Event (AE) Log.

8.10.1 Device-Related Adverse Event (AE)

This registry will only collect device-related adverse events. A device-related adverse event is defined as any untoward medical occurrence in the subject that is associated with the use of the Flexitouch system or Flexitouch Plus.

Adverse events will be reported to the IRB in accordance with IRB policy.

8.10.2 Serious Adverse Event (SAE)

A serious adverse event is an untoward medical occurrence where the outcome is:

- Death;
- Life-threatening event (places the subject at immediate risk of death from the experience as it occurred);
- Hospitalization (initial or prolonged) if admission to hospital was warranted as a result of an adverse event;
- Disability or permanent damage (substantial disruption of one's ability to carry out normal life functions);
- Congenital anomaly or birth defect;
- Required intervention to prevent permanent impairment or damage;
- or
- Important medical event that required medical or interventional treatment to prevent one of the previous outcomes.

Investigators must report all device-related, Serious Adverse Events (SAEs) to Tactile Medical within 10 work days of becoming aware of the event. Device-related SAEs will be summarized in writing and reported to the IRB in accordance with IRB policy.

8.10.3 Device Observations

Device observations will be recorded and reported to Tactile Medical. Device observations include device failures, device malfunctions, use errors, device issues, and user preferences, as defined below:

- **Device Failure:** A device failure has occurred when the device is used in accordance with the IFU, but does not perform as described in the IFU and also negatively impacts treatment of the study subject.
- **Device Malfunction:** A device malfunction occurs when an unexpected change to the device that is contradictory to the IFU is observed, which may or may not affect device performance.
- **Use Error:** A device use error is an act or omission of an act that results in a different medical device response than intended by the manufacturer or expected by the user. Use error includes slips, lapses, and mistakes. An unexpected physiological response of the subject does not itself constitute a use error.
- **Device Issue:** Any other issue with the device that does not fall into one of the above categories.
- **User Preference:** Information on user expectations, likes, dislikes, motivations, and inclinations that drive subject satisfaction with the device.

9.0 Subject Withdrawal or Early Termination

Subject participation may be terminated prior to completing the registry for any of the following reasons:

- **Withdrawal of Consent**
Subjects may withdraw their consent to participate at any time. If a subject withdraws consent, previous information that has already been obtained will be available for analysis.
- **Lost to Follow-up**
A certified, return-receipt letter must be sent to the subject after 2 attempts to reach the subject by telephone have failed. The subject will be considered lost to follow-up if this communication is unsuccessful.
- **Adverse Event**
Subject experiences an adverse event that in the investigator's clinical judgement necessitates discontinuation of their participation in this registry.
- **Discretion of the Principal Investigator**
Subjects may be withdrawn at the investigator's discretion in the event of subject noncompliance, changes in the subject's health, or other reasons based on the investigator's clinical judgment.

When a subject withdraws prior to completing the registry, all effort should be made to complete Visit 7 prior to documenting the reason for withdrawal in the subject's medical record.

10.0 Device Accountability

To participate in the registry, the Flexitouch system or Flexitouch Plus must be prescribed by a clinician and paid for by the subject or their payer. The Flexitouch system or Flexitouch Plus will be provided to the subject and tracked according to normal business practices at Tactile Medical.

11.0 Risk Analysis and Adverse Events

Pneumatic compression is a minimal risk therapy with minimal known complications or adverse events. However, as with any treatment, there is the possibility of undesirable events such as a local skin reaction to the device materials. The subject will be made aware of known complications and adverse events at the time of consent, and monitored closely throughout the registry.

There are nominal possible adverse effects associated with the therapy. The expected adverse effects that are experienced by patients using this device are often due to the natural history of the primary disease, or a failure to achieve an adequate response to the compressive therapeutic intervention, and are thus not related to the therapy itself. In some cases, lymphedema adverse events can be serious, long lasting, or may be permanent. The risks listed below are symptoms or signs of lymphedema and may be experienced by all subjects with lymphedema:

Likely:

- Pain or discomfort
- Increased swelling

Less Likely:

- Cellulitis – Infection of the skin which may include swelling, redness, and tenderness of the infected tissue
- New or increased edema in the trunk and/or genital region

Registry subjects will be informed of any significant new findings that develop during the course of this registry that may affect their willingness to continue participation. The Principal Investigator will oversee all safety aspects of the registry and report all adverse events to the IRB. Should a subject choose to terminate his or her participation in the registry, he or she will be treated according to the standard of care that applies at the point of withdrawal.

12.0 Provisions to Protect the Privacy of Registry Participants/Information Security Plan

This research represents a registry documenting head and neck lymphedema. The most likely risk posed to participants would be a breach of confidentiality if someone other than the research team obtained access to the data.

There are security measures in place to prevent a breach of confidentiality from happening including password protected electronic database and the use of subject codes to de-identify data).

Precautions will be taken to make sure that only authorized individuals will be accessing subject research records. The collection of sensitive information about subjects is limited to the amount necessary to achieve the aims of the research registry, so that no unneeded sensitive information is being collected. The Information Security Plan, per the requirements of VHA Handbook 1200.05 include, but are not limited to, the following provisions:

- a. Individually identifiable information will be collected and used in accordance with ICH GCP
- b. Data are to be collected via clinical research forms

- c. Data will be stored at the Investigation Site and at the Company in accordance with ICH GCP and retained in accordance with the Company's Policy 30 (Record Retention Policy)
- d. Data will be transported or transmitted from one location to another via Federal Express or secure email in accordance with the Company's internal Policy 45 (Confidentiality and Privacy of Patient Information) and Policy 91 (Data Transmission)
- e. The PI, Company clinical research team, and authorized Site personnel will have access to the data and thus are responsible for its security
- f. Company will abide by all HIPAA regulations when considering Business Associates or downstream entities that may have access to data
- g. The Coordinating Center, Investigation Site, PI, and Company clinical research team will have access to and be responsible for the security of the information. Company will abide by its internal Policy 45 (Confidentiality and Privacy of Patient Information)
- h. Medical records, verbal reports, and clinical research forms will account for the information
- i. Company will follow guidelines established by the Company (Policy 45), ICH GCP, and HIPAA to ensure security measures are in place to protect individually identifiable information
- j. If VA information is suspected or confirmed lost, a report will be filed with the Department of Veterans Affairs, Office of the Inspector General at <https://www.va.gov/oig/hotline/>

13.0 Deviation from Registry Plan

All deviations will be documented on the Deviation Log and reported to the IRB as required by IRB policies.

14.0 Quality Assurance Procedures

This registry will be conducted in accordance to all applicable regulations. Good Clinical Practice (GCP) (GCP E6 R2) will be used as a guidance for the preparation and conduct of the clinical registry.

14.1 Site Qualification

Tactile Medical personnel will conduct a Qualification Visit onsite or by telephone to verify the resources, staffing, and subject pool are adequate to ensure successful enrollment and registry completion.

14.2 Site Initiation

Tactile Medical personnel will conduct a Site Initiation Visit onsite or by telephone to ensure all required regulatory documents are accurate and complete, and site personnel has been adequately trained on the registry protocol. An activation letter will be sent to the Principal Investigator once the site is approved to enroll subjects.

14.3 Data Collection Procedures

Raw data will be collected on appropriate source document worksheets and CRFs will be submitted to Tactile Medical for data entry. Alternatively, at some point

during the registry, source document data may be entered directly into a validated and secure electronic data capture (EDC) system by trained site personnel.

14.4 Onsite Monitoring

Clinical sites will be monitored for compliance with the clinical protocol, investigator agreement, and applicable regulations throughout the registry. Prior to each visit, the investigator will receive a confirmation letter outlining the scheduled dates and activities.

Regular site contact will be maintained to ensure:

- Subject safety;
- Clinical site staff are well informed of regulations and sponsor requirements;
- The clinical protocol is followed;
- Data are gathered in a complete and timely manner;
- Problems with data or data collection are addressed appropriately and in a timely manner;
- Adverse events are properly reported in a timely manner; and
- Each onsite visit is recorded on the Site Visit Log.

After each visit, the investigator will receive a follow-up letter summarizing site progress as well as any outstanding items that need to be addressed.

In addition to site visits, a screening log must be submitted to Tactile Medical as requested (by fax or e-mail). This screening log should be reviewed with site staff to assess planned versus actual recruitment.

The Principal Investigator and Institution agree to permit trial related monitoring, audits, IRB review, and regulatory inspection(s); providing direct access to source data and documents, as appropriate. Monitoring and source verification will be performed by a Tactile Medical CRA and/or designee. Source verification includes reviewing subject source documentation and Case Report Forms (CRFs) for accuracy, completeness, and compliance with GCP.

14.5 Data Safety Monitoring

A periodic review may be completed by a designated member of the Scientific Advisory Board or the Chief Medical Officer at Tactile Medical. The frequency of the review will be determined based on a number of parameters including, but not limited to: the rate of enrollment, number of AEs and/or SAEs, and number of significant deviations from the protocol. At the conclusion of the review, the reviewer may provide recommendations pertaining to registry continuation, modification, or termination of the trial or investigational site.

14.6 Reports and Records

Records to be maintained by the investigator in a designated registry file include:

- Investigational plan and all amendments;
- Signed Investigator Agreement/Research Contract;

- IRB approval letter, including a copy of the approved consent forms, progress reports, and adverse event reports;
- IRB roster or Assurance number, if applicable;
- All correspondence relating to the conduct of this registry between the site and sponsor, IRB, and registry monitor;
- Curriculum Vitae and professional license for all registry personnel, if applicable;
- Site personnel signature and documentation regarding the investigator's delegation of responsibility;
- Site visit log;
- Protocol/device related training records for all applicable registry personnel;
- Screening log; and
- Reports (shown below).

The Principal Investigator is required to prepare and submit to Tactile Medical, or its designees, complete, accurate, and timely reports on this investigation as required by regulations. These reports include:

Reports	Submit To	Timeframe
Device-Related AE	Sponsor and Reviewing IRB	Sponsor: Within 15 working days of becoming aware of the event; IRB: In accordance with IRB procedure.
SAE	Sponsor and Reviewing IRB	Sponsor: Within 10 working days of becoming aware of the event; IRB: In accordance with IRB procedure.
Withdrawal of IRB Approval	Sponsor	Within 5 working days
Progress	Sponsor and Reviewing IRB	Annually, at a minimum
Final	Sponsor and Reviewing IRB	Within 3 months following the completion or termination of the Investigator's part

The following records must be maintained for each subject enrolled:

- Original, signed and dated informed consent form, as well as documentation of the process of consent;
- Completed CRFs, queries, and source document worksheets, as applicable; and

- Complete medical records including procedure reports, lab reports, etc., as applicable.

Subject registry records, correspondence files, all supporting registry documentation, and reports must remain on file at the site for a minimum of ten years after the conclusion of this registry. All investigators must contact Tactile Medical personnel prior to destroying or archiving off-site any records and reports pertaining to this registry to ensure that they no longer need to be retained on-site. Additionally, Tactile Medical personnel must be contacted if the investigator plans to leave the investigational site to ensure that arrangements for a new investigator or records transfer are made prior to the investigator's departure.

15.0 Statistical Methods

For continuous variables, descriptive statistics will include the number of subjects (n), mean, standard deviation, median, inter-quartile range, minimum, and maximum, based upon subjects with reported data for the variable being analyzed.

Frequencies (numerator and denominator), percentages, and 95% confidence intervals will be displayed for categorical data. Percentages by categories will be based on the number of subjects with no missing (unreported) data for the specific variable being analyzed and the count of the patients for each individual level of the categorical variable (the level specific numerators). Percentages will add up to 100%, unless otherwise indicated.

There are no plans to impute missing data and there are no plans to explicitly report missing data (counts and/or percentages) in the tables for all variables as part of the planned study report content. Variations in the reported sample sizes within and/or between relevant tables can be used to ascertain insights into unreported data. In some cases, unreported data may be due to it not being clinically relevant to a particular patient or may represent expected data that was not collected. Selected analyses pertaining to unreported and/or missing data may be discussed and considered as future findings warrant.

The observational nature of the study suggests that the statistical focus will be on estimation and hypothesis generation and not hypothesis testing. Though p-values will be reported as apropos, point estimates, and 95% confidence intervals will be used to guide exploratory analyses for potentially clinically meaningful differences or changes to be discussed and evaluated.

Inter-group (e.g., bivariate) comparisons, when performed, will utilize chi-square, ANOVA, t-test, and appropriate non-parametric tests, unless otherwise specified.

Multivariable models (e.g., linear regression or logistic regression) may be used to assess the predictive relationships and control for possible confounding imbalances of selected multiple variables to specific outcome measures of interest.

Any formal null hypothesis-based statistical comparisons will be made using two sided tests at the $\alpha=0.05$ significance level unless specifically stated otherwise. All null hypotheses will be of no inter-group difference, all alternative hypotheses will be two-sided, unless specifically stated otherwise.

All data processing, summarization, and analyses will be performed using R Version 3.4.0 or higher.

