5.1 Endpoints

5.1.1 Primary Endpoints

To evaluate symptom and function improvement after 168 days (approximately 6 months) of treatment with the Flexitouch system or Flexitouch Plus based upon:

- Symptom survey (EORTC H+N35); and
- Range of motion measures (neck, mouth, and shoulder).

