5.1.2 Secondary Endpoints

To evaluate quality of life (QOL), pain, swelling, ease of use, and treatment satisfaction after 168 days (approximately 6 months) of treatment with the Flexitouch system or Flexitouch Plus based upon:

- Change in the QOL (EORTC C30);
- Change in pain (VAS);
- Change in swelling (upper neck, lower neck, and ear to ear measurements); and
- Ease of use and treatment satisfaction (survey).

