5.2 Subject Selection

The registry population will be drawn from patients who have head and neck lymphedema and are prescribed the Flexitouch system or Flexitouch Plus for in-home treatment of their head and neck lymphedema. Only patients who meet the criteria listed below and have provided informed consent will be considered for participation. Subjects will be considered enrolled in the study after they have signed the Informed Consent Form, met all inclusion/exclusion criteria, and completed the device training visit. Any subjects who do not meet inclusion/exclusion criteria, or do not ultimately receive the device, will be considered screen failures.

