5.3 Registry Duration

Enrollment will occur at centers throughout the United States. Subjects will remain active in the registry for a period of 168 days (approximately 6 months), and after that time, no additional information will be collected. The duration of the registry has not been specified; however, enrollment will be open for the duration of the registry. Registry analyses will be completed at various times throughout the lifecycle of the project.

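### Day 168 results rest on subjects with reported data, with no specified missing-data analysis and no analysis rule for an early-termination Visit 7, so the six-month estimate can be biased by an unknown amount

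*Combined protocol and SAP*

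**What the plan says.** Section 15.0 (Statistical Methods) describes continuous variables "based upon subjects with reported data for the variable being analyzed", and percentages likewise use non-missing denominators. It adds, of tables covering every variable: "There are no plans to impute missing data and there are no plans to explicitly report missing data (counts and/or percentages) in the tables". Readers are to judge missingness from how the sample sizes vary between tables. Further work is left open: "Selected analyses pertaining to unreported and/or missing data may be discussed and considered as future findings warrant". Multivariable models are permitted, for prediction and confounding. The stated focus is estimation, in which "point estimates, and 95% confidence intervals will be used to guide exploratory analyses for potentially clinically meaningful differences or changes" are to be discussed.

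The primary endpoint (5.1.1) is "To evaluate symptom and function improvement after 168 days (approximately 6 months) of treatment", measured by the EORTC H+N35 and range of motion. The pain, swelling and quality-of-life secondary endpoints (5.1.2) are worded as changes; the first begins "Change in the QOL (EORTC C30".

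Sections 6.7 and 9.0 have Visit 7 attempted when a subject leaves early, as well as at Day 168±14. Section 6.8 records the date and reason for exit. Section 5.3 keeps enrollment open and states: "Registry analyses will be completed at various times throughout the lifecycle of the project".

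**The concern.** The registry has one cohort and no control group, and its main product is an estimate of change at six months. Section 9.0 allows exit for adverse events, noncompliance and changes in health. If leavers would have changed differently from stayers, a summary of those with data does not describe those enrolled. Open enrollment narrows the confidence interval but leaves that bias in place.

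Two definitions needed for the Day 168 estimate are missing:

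- **Paired or unpaired.** Paired change is the natural reading of the secondary endpoints, but 5.1.1 says only improvement. If Baseline and Day 168 are each summarised in whoever reported them, the two means describe different people.
- **Early Visit 7.** There is a conduct rule (attempt the visit) but no analysis rule. Two analysts could defensibly give different Day 168 results from the same data.

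In addition, at an interim data cut a lower n mixes subjects not yet due, subjects lost, and items not applicable.

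**Working it through.** **Inputs from the documents.** Range of motion, swelling, H+N35, C30 and VAS are collected at Baseline and Days 28, 84 and 168 (section 7.0). The windows are Day 28±5, Day 84±5 and Day 168±14. Sample size is open (Synopsis). No dropout rate, SD or expected change is given, so there is no plan figure to reproduce and every size below rests on assumptions.

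**Step 1: general formula.** With a fraction m missing,

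bias = m × (mean change in observed − mean change in missing).

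Assume the two means differ by 0.5 SD of the change. The bias is then 0.05, 0.10, 0.15 and 0.20 SD at m = 10, 20, 30 and 40%. Its sign follows the sign of the difference, and it is zero if loss is unrelated to change. At m = 30%:

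- 100 enrolled: 70 observed, 95% half-width 1.96/√70 = 0.234, coverage about 76%.
- 200 enrolled: 140 observed, half-width 1.96/√140 = 0.166, coverage about 57%.

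The bias is 0.15 in both, so coverage worsens as the registry grows.

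**Step 2: simulation.** Assumptions: visit means 0, -0.10, -0.20, -0.30 (negative is improvement), unit variances, all correlations 0.6, and 25% missing at Day 168 by a logistic rule with the stated odds ratio (OR) per SD of the driver. Truth is -0.30. *Paired* is the within-subject change in completers. *Unpaired* is the Day 168 mean in reporters minus the Baseline mean in all enrolled. *Model* is a likelihood estimate from all four visits. Entries are for OR 1.35 / 2 / 3.5.

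| Loss depends on | Paired | Unpaired | Model |
|---|---|---|---|
| Baseline severity | -0.27 / -0.24 / -0.20 | -0.35 / -0.40 / -0.45 | -0.30 each |
| Day 84 change, non-improvers leave | -0.33 / -0.37 / -0.41 | -0.30 each | -0.30 each |
| Day 84 change, improvers leave | -0.27 / -0.23 / -0.19 | -0.30 each | -0.30 each |
| Unobserved Day 168 change | -0.37 / -0.44 / -0.52 | -0.33 / -0.37 / -0.41 | -0.34 / -0.39 / -0.45 |

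Under random loss the paired and model estimates are both -0.30. Three things follow:

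- Baseline-driven loss understates improvement if change is paired and overstates it if unpaired, so the unwritten definition decides the direction.
- In the last row the model cuts the paired bias from 0.066 to 0.043, 0.142 to 0.093 and 0.223 to 0.151, which is about a third.
- At n = 200 the paired half-width is 1.96 × √(0.8/150) = 0.143. For the first three rows, coverage is 92-93% at OR 1.35 and 65-71% at OR 3.5. Weak dependence therefore matters little at that size.

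**Step 3: early Visit 7.** Before Day 154 the clinic windows cover Days 23-33 and 79-89, which is 22 of 153 days. The other 131 (86%) lie in no window. Assume (positive is improvement) completers change 0.50 SD, 30% leave, and half of those attend an early visit. Counting those visits as Day 168 gives (0.70 × 0.50 + 0.15 × x)/0.85, where x is the early leavers' change. This is 0.37 for x = -0.25 and 0.54 for x = +0.75, against 0.50 if they are left out.

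Dropping early values has a cost too. With exits near Day 56 driven by the change at that time, and the Step 2 truth of -0.30, a model without those values gives -0.313 / -0.326 / -0.345. Counting them as Day 168 gives -0.239 / -0.208 / -0.179.

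**Step 4: data cuts.** A valid Visit 7 can occur from Day 154, and the window closes on Day 168 + 14 = Day 182. If only the due count waits for Day 182, the observed count can exceed it. Both counts need the same restriction.

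**The case against.** The strongest reply is that this is a descriptive registry. Section 15.0 puts estimation and hypothesis generation ahead of testing, shows n and denominators, and leaves room for missing-data analyses. Exit date and reason are recorded, so attrition could be reconstructed. That lowers the stakes. It does not remove the point, because bias affects an estimate directly and a missing-data analysis chosen after the findings are seen is weak protection. An n alone also gives no reasons for loss.

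A second reply is that the model is not best in every case. This stands. Its exact recovery of -0.30 is built in, since the data were generated from the model that is fitted and loss depended only on observed values. Under unobserved-outcome loss the unpaired contrast lies nearer the truth. That result, and the absence of unpaired bias under Day 84-driven loss, come from the equal-correlation set-up: the covariance of the Day 168 value with the Day 84 change is 0.6 − 0.6 = 0. The documents do not support equal correlations, so this is no reason to prefer an unpaired contrast between different people.

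A reader might also infer that the plan overstates benefit, or that it conceals missing data. Neither is supported. The exit reasons make overstatement plausible, but no figure fixes the direction. The sentence on missing counts refers to the tables for all variables, and sample sizes are shown.

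**Conclusion.** The concern holds and should be fixed. Followed as written, the plan can give a biased Day 168 estimate whose size and direction cannot be determined from the documents. The figures above depend on assumed dropout, correlation and loss mechanism. The coverage figures further assume that change is analysed paired, or as reported change scores, so they illustrate the problem and do not predict this registry's results. It would also go too far to say that early termination is unaddressed, since the visit is to be attempted and only its analysis is undefined. Nor may one conclude that a repeated-measures model would remove the bias: it corrects loss explained by observed values, and only part of any loss that depends on unobserved outcomes.

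**What to change.** Add three rules to section 15.0.

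1. **Estimator.** Define Day 168 change as within-subject Visit 7 minus Baseline. For continuous measures, report a likelihood-based repeated-measures estimate from Baseline and Days 28, 84 and 168, in all enrolled subjects (as defined in 5.2) with any of these data. Show it beside the paired summary. State its limit for loss that depends on unobserved outcomes, and add a shift-type sensitivity analysis reported as a range.
2. **Early Visit 7.** Do not label a value outside Day 168±14 as Day 168 in the main estimate. Analyse it at its actual day, either assigned to the clinic window it falls in or with actual day as the time variable in a sensitivity model, so that leavers' data are not discarded.
3. **Attrition.** For each primary and secondary measure, tabulate by visit the numbers enrolled, due, observed, and missing with exit reason. At a data cut, restrict both due and observed to subjects whose window has closed (Day 182 for Visit 7), and show those not yet due separately. Compare baseline values of subjects with and without Day 168 data.

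The ease-of-use survey is taken only at Visit 7, so rule 2's bar on labelling early values as Day 168 and rule 3 apply to it, but the model does not.

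Cost: statistical wording, one extra model per continuous measure and one table per measure, with no new visits or assessments. The reported benefit may turn out less favourable.
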